1.2 Schema

Screening participants by inclusion and exclusion criteria **Pre-operative** Obtaining informed consent, Enrolling participants **Clinic Visit Demographics Questionnaire** Surgery, Inpatient Recovery Randomization Apixaban Enoxaparin Discharge At home, self-administration of anticoagulant Phone Call #1: • Medication counting **POD 30** PROMIS, Patient Satisfaction Questionnaire (end of Chart review for perioperative variables & pharmacy prophylactic cost data anticoagulation) Screening for VTE & bleeding Phone Call #2: **POD 90** • COST Questionnaire Screening for VTE & bleeding

2 INTRODUCTION AND BACKGROUND

2.1 Study Rationale

Venous thromboembolism (VTE), including both deep venous thrombosis (DVT) and pulmonary embolism (PE), after radical cystectomy (RC) constitutes a significant burden on bladder cancer patients in terms of morbidity, mortality, and cost. PE is one of the most common causes of perioperative mortality after RC, reported to be 16% in one study.³ Patients diagnosed with DVT or PE require at least six months of anticoagulation and treatment, resulting in burdensome medication use and followup appointments. The annual per-patient cost of DVT or PE has been reported as high as \$3,000 or \$6,000, respectively.⁴ Prior analyses of large datasets suggest the incidence of symptomatic VTE ranges from 2-12% in the first 30 days after surgery, ⁵⁻¹² and data confirm the risk is sustained after hospital discharge. ^{5,9,10,12}

Growing recognition of this burden led to the practice of extending the period of pharmacologic prophylaxis against VTE beyond just the patient's inpatient stay so that the patient continues prophylaxis until the 30th postoperative day (POD). This practice is well established and codified into many surgical oncologic guidelines, both urologic and others. The data supporting the practice in oncologic surgery populations are quite robust; a recent Cochrane Review of seven randomized, controlled trials of patients postop from abdominal and pelvic oncologic operations shows the rate of VTE was reduced from 13% in the non-prophylaxis group to 5.3% in the group receiving the blood thinner enoxaparin for 28 days after surgery.¹³

Regarding the bladder cancer population and RC specifically, a single institution study of over 400 patients showed a decrease in VTE rate from 12% to 5% after instituting the practice of 28 days of enoxaparin after discharge, ¹⁴ and a more recent study showed an even bigger decrease from 17.6% to 5.06% in the 90 days after discharge. ¹⁵ The European Association of Urology (EAU) has thus adopted a recommendation stating, "the optimal duration of pharmacological prophylaxis is approximately four weeks post-surgery." ¹⁶

In the face of the mounting evidence and these emerging guidelines, the practice of extended VTE prophylaxis has rapidly expanded in the past several years and become standard of care. An analysis of the Optum database of prescription data suggests the practice of prescribing enoxaparin after discharge after RC increased from only 9% of cases in 2012 to 26% in 2017.¹⁷ Even more recently, a 2020 survey of 121 physician members of the Society of Urologic Oncology (SUO) reported 80% endorsed the use of extended prophylaxis (EP) for this duration.¹⁸

There are still several barriers that exist to the full adoption of discharge on enoxaparin injections. In addition to the eligibility restrictions based on renal function, patients continue to face significant operational and quality of life barriers, including issues related to insurance coverage, cost, as well as the pain and discomfort experienced during self-injections. In the described SUO survey, half of providers that prescribe EP report experiencing issues with lack of

insurance coverage for enoxaparin injections (38%), inability of patients to afford the medication (51%), and need to perform cumbersome additional insurance authorization processes (44%). Approximately 20% report issues with patient adherence and refusal to perform the enoxaparin injections. The providers who elected not to prescribe EP correspondingly cited these as reasons they elected not to use it. ¹⁹ Similar reports exist in non-urologic cancer surgery; among those surgeons who were noncompliant with EP guidelines for pancreatic and hepatobiliary surgeries, the most significant barriers reported were "drug cost," "subcutaneous injections, and "logistical challenges of prescribing." ²⁰

Direct Oral Anticoagulants (DOACs), specifically apixaban, have recently emerged as a viable option for providing pharmacologic VTE prophylaxis to patients after discharge while avoiding some of the persistent issues encountered with discharge on enoxaparin. Gynecologic oncologists have been early adopters of this practice and their pelvic cancer surgeries offer a reasonable comparator to RC. In a recent trial, 400 women undergoing gynecologic cancer surgery were randomized to 28 days of either prophylactic enoxaparin or apixaban with results showing there were no differences between groups for rates of major bleeding or venous thromboembolic events but patients in the apixaban group reported increased ease and decreased pain associated with taking the medication.²¹ There is even stronger data supporting the efficacy of apixaban as compared to enoxaparin in the orthopedic field, with a randomized trial of over 3,000 patients showing a 15% VTE rate using apixaban as EP compared to 24% using enoxaparin.²²

2.2 Previous Literature

In the urologic field, there have been only a handful of exceedingly small, retrospective studies investigating the feasibility of using apixaban after discharge. 23–25 Urologists from the University of Missouri and St. Louis University initiated a quality improvement pathway for recovery after RC which included prescribing apixaban at discharge until POD 28. Their retrospective review of 72 patients who completed the apixaban protocol showed no increase in rates of DVT, major bleeding, or other complications compared to their historical rates.²⁵ The Mayo clinic in Arizona similarly made an institutional change to using a DOAC rather than enoxaparin as EP in 2019 and performed a retrospective comparison of 46 patients who received a DOAC, 55 patients who received enoxaparin and 556 patients who received no EP (from either before or after 2019). Their results show VTE rates of 0%, 3.6% and 7.2% in the cohorts who received a DOAC, enoxaparin, and no VTE prophylaxis, respectively (p=0.11). They also indicate no significant difference in GI bleeding among the three groups.²³ Looking specifically at patients who underwent robot-assisted radical cystectomy at another academic center, Ortiz et al. perform a retrospective comparison enoxaparin vs DOACs following an institutional change to using DOACs. Of 66 patients included in their review, their data show DVT rates of 3/37 patients in the enoxaparin arm vs 1/29 in the DOAC arm; a difference which was not statistically

significant. They also show no statistical difference in postoperative complication rates including ED returns, readmissions, bleeding events, or wound complications.^{24,25}

The largest of these types of retrospective cohort studies was performed by Westerman et al. at MD Anderson in 2021. Similarly, it is a retrospective comparison of the outcomes following an institutional change from the use of enoxaparin to the use of apixaban; Westerman et al. capture 145 patients in each phase. Their results suggest a possibly improved DVT rate on apixaban (0% vs 3.1%) following the switch, as well as fewer compliance "events" (0% with apixaban vs 33.5% with enoxaparin). Notably, this was not a randomized study, not all patients who were discharged on prophylaxis had undergone RC, and not all patients who underwent RC were discharged on prophylaxis; apixaban was simply used in urologic cancer cases where surgeon discretion would have led to discharge on enoxaparin prophylaxis.

In summary, the clinical benefit of extended prophylaxis in reducing venous thromboembolism (VTE) immediately after major abdominal oncologic surgery is evident. The use of DOACs as a substitute for enoxaparin has been extensively studied in non-urologic cancer patients, but its adoption by urologic cancer surgeons is still in the early stages. While several small retrospective reports have been published, demonstrating the safety outcomes of switching to DOACs as EP, the potential advantages of using DOACs to mitigate the issues associated with enoxaparin self-injection and enhance patient adherence and accessibility to these medications remain unexplored.

2.3 Preliminary Institutional Results

Given the earlier data suggesting barriers to adoption include cost, we sought to assess the state of prescription costs at our institution and determine how likely this is to pose a barrier to patient adherence. We reviewed our institution's outpatient pharmacy data from July to December of 2022, including the copays that patients being discharged on prophylactic dose apixaban and enoxaparin face at our institution as well as difficulties encountered with prior authorizations. Data suggest that copays may vary from as low as \$0 to >\$100, and that copays are much more likely to be increased with apixaban (Table 1). Review of prior authorizations show that a substantial number of prior authorizations were submitted, and in particular that denial of these prior authorizations and insurance coverage may pose a problem for both medications, in particular apixaban (Table 2).

Table 1. Patient copays for Enoxaparin and Apixaban

Lovenox PX (30mg & 40mg QD	
Copay (\$)	Count
0	103
0-20	108
21-50	27
51-100	14
>100	17
Total	269

Apixaban PX (2.5mg BID)		
Copay (\$)	Count	
0	15	
0-20	14	
21-50	11	
51-100	3	
>100	4	
Total	47	

Table 2. Outcomes of prior authorizations submitted for Enoxaparin and Apixaban

Prior Authorizations					
Medication	Approved	Denied	Total		
Apixaban	32	9	41		
Lovenox	19	2	21		

3 STUDY OBJECTIVES AND ENDPOINTS

OBJECTIVES	ENDPOINTS	JUSTIFICATION FOR ENDPOINTS
Primary		
To compare rates of adherence to discharge on enoxaparin vs apixaban	Proportion of days covered (PDC). This will be calculated based on the size of prescription the patient was provided, day of surgery, day of discharge, and how many pills/syringes are remaining at POD30.	This is an objective and quantitative way to measure adherence.
Secondary		
To explore possible reasons for adherence vs non adherence	PROMIS Medication Adherence Scale: a nine-item questionnaire ^{26,27}	This is a validated measure of medication adherence that focuses on the possible reasons for non-adherence
	Participant satisfaction	Participants will answer questions specific to the use of enoxaparin and apixaban at home after RC. These questions were selected based on the clinical experience of the PIs as well as other studies that have examined adherence to enoxaparin and apixaban ^{21,27,28}
	COST-FACIT: a 12-item questionnaire ²	This is a questionnaire that was developed and validated in the cancer population for assessing patient-reported financial distress due to healthcare costs. This questionnaire adds a patient reported component, as simple cost data does not capture how burdensome that cost is to each specific patient
To compare the cost of enoxaparin vs apixaban	Out of pocket cost of prescription for anticoagulant, in dollars	This provides objective measure of the cost comparison between enoxaparin and apixaban. This data combined with adherence data may allow providers to determine the most cost effective option.

OBJECTIVES	ENDPOINTS	JUSTIFICATION FOR ENDPOINTS
Tertiary		
To collect mefficacy and safety data regarding both forms of prophylaxis	Rate of VTE, either PE or DVT Rate of bleeding events, classified as major, clinically relevant nonmajor, or nonmajor.	While data suggest VTE rates are comparable between enoxaparin and apixaban in both non-urologic and urologic studies, the urologic studies are in small populations. We therefore plan to track VTE and bleeding as outcomes to continue contributing to the pool of data. These outcomes would likely have been measured even if they were not outcomes as part of safety monitoring.

4 STUDY DESIGN

This is a pragmatic, multi-site, randomized, controlled trial comparing two anticoagulant medications, enoxaparin and apixaban, when given to bladder cancer patients as VTE prophylaxis after RC.

The primary objective of the study is to assess participant adherence to the at-home anticoagulation regimen. Other objectives include participant satisfaction and cost burden. At 30 days postop study team members will call participants to assess the primary endpoint of adherence as well as secondary endpoints of cost and patient satisfaction. At 90 days the participants will receive another phone call to complete one additional questionnaire assessing financial burden since surgery. While both drugs are considered standard of care for EP after RC, apixaban is considered the intervention arm due to its more recent introduction and use at this institution. The study is powered to detect if adherence to apixaban is noninferior to enoxaparin. If this criterion is met the study will also test for the superiority of apixaban.

4.1 Minimizing Bias

Patients will be randomized to a prescription for one of the two anticoagulants at the time of postoperative discharge, and instructed to continue the medication until POD30. Randomization will be performed in a simple 1:1 fashion.

The randomization will be non-blinded. Given that this trial aims to explore the real experience of patients on these medications, blinding and placebo would actually detract from the important clinical context and understanding that participants have. Furthermore, enoxaparin and apixaban have different routes of administration (enoxaparin is injectable and apixaban is oral) which makes blinding and placebo infeasible. Blinding of the investigators is not necessary given the outcomes are patient reported surveys and pill/vial counts. Bias will be sufficiently reduced by randomization.

The University of Pennsylvania will serve as the primary site, and Vanderbilt University Medical Center as a second site. The addition of a second site will also introduce variety into the study population and strengthen its applicability.

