5.3 Recruitment

The University of Pennsylvania historically performs ~70 cystectomies per year. Vanderbilt University Medical Center performs ~90 per year. To achieve the target analysis group of 90 patients we plan to enroll 108 (see section 9.3.1). Thus the planned recruitment/enrollment period is approximately 12 months.

Recruitment will take place in outpatient offices. We will review the medical charts of patients seeing our Urologic oncology surgeons a week ahead of time and flag charts that suggest a radical cystectomy may be an indicated therapy for a patient. Staff will plan to be available on these days to screen and enroll as able.

The treating physician will discuss post-operative extended prophylaxis (EP) with anticoagulants with the patient during their visit because it is standard of care. Within this context the treating physician will introduce the option to participate in the trial and undergo randomization between forms of EP, however it will be made clear to the potential participant that they will receive standard of care EP regardless of their choice to participate or not.

After the visit, further discussion of the trial and screening will be performed by trial staff other than the treating physician, and participants will be allowed to think about their decision after the initial discussion and enroll at a later date (as long as they enroll prior to undergoing surgery). Both of these features will help further mitigate any undue pressure patients may feel. If a patient cannot be approached in person or decides they would like to think longer about their decision to participate, a member of the research team will contact them by phone and complete the remaining enrollment process over the phone and electronically.

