10.7 Compensation

Participants at the University of Pennsylvania will be given a \$20 Greenphire ClinCard, either electronic or physically mailed based on patient preference, at the completion of the study as a gesture of thanks for their time in participating. Receipt is contingent only on completing both study visits. This effort is supported by the American Urologic Association Resident Research Award.

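### Simple 1:1 allocation at two sites, with no site term in any analysis, leaves a small, avoidable loss of precision (not a bias) that site-stratified blocks and site-adjusted comparisons would remove

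*Combined protocol and SAP*

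**What the plan says.** Section 4.1 sets the allocation: "Patients will be randomized to a prescription for one of the two anticoagulants at the time of postoperative discharge", and "Randomization will be performed in a simple 1:1 fashion". Blocks, strata and minimisation are not mentioned anywhere. The same section names two sites, "The University of Pennsylvania will serve as the primary site, and Vanderbilt University Medical Center as a second site", and gives the reason for the second: "The addition of a second site will also introduce variety into the study population". Section 5.3 gives the volumes, "The University of Pennsylvania historically performs ~70 cystectomies per year. Vanderbilt University Medical Center performs ~90 per year", and the targets of 108 enrolled and 90 analysed.

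Site appears in no planned comparison:

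- Section 9.3 uses a pooled two-group difference in proportions for PDC.
- Section 9.4 uses a test of proportions, a rank sum test for cost, and a t test (or rank sum) for questionnaire scores.
- The long covariate list in Section 9.5 omits site.

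Section 9.7 discards missing data from all analyses. Section 10.7 describes a $20 card for participants at the University of Pennsylvania: "Receipt is contingent only on completing both study visits". It is silent about the other site.

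**The concern.** With about 100 patients, unrestricted allocation can leave the arms noticeably unequal in size and in site mix. If PDC, out-of-pocket cost or completion of visits differs between the two hospitals, an uneven site mix moves the observed arm difference in that particular trial, and nothing in the analysis takes the movement out. Cost is the endpoint most plausibly tied to site, but the only copay table (Section 2.3) comes from one institution, so its site dependence cannot be sized. What is at stake is some precision in a small non-inferiority trial, and how easily a reader can attribute a difference to drug rather than hospital.

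**Working it through.** **The plan's own figure.** Section 9.3.1 gives 45 per arm for control PDC 0.85, margin 0.15, one-sided 0.05 and 80% power. The binary formula gives n = (1.645 + 0.842)² × 2 × 0.85 × 0.15 / 0.15² ≈ 70.1, so 71 per arm, not 45. PDC treated as a continuous mean gives 45 per arm if the SD is 0.15 × √(45/2) / (1.645 + 0.842) ≈ 0.286. The plan states no SD. I use 0.286 only so that the power figures start near the plan's 80%. The mismatch in sample size is a separate and larger matter.

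**Inputs.** N = 90 and 108 (Section 5.3). Site split 70:90, which gives 39:51 at N=90 and 47:61 at N=108. These are surgical volumes, not projected enrolment, so the split is an assumption. Site gap in mean PDC of 0, 0.10 or 0.20, also assumed, because the documents give none.

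**Arm size.** One arm's size is Binomial(N, 0.5).

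- P(arms differ by 10 or more) = 34% at N=90 and 39% at N=108.
- A 50:40 split keeps 4 × 50 × 40 / 90² = 98.8% of the information of 45:45.
- Averaged over allocations, unequal arms lower power from 80.1% to 79.7% (N=90) and from 86.1% to 85.8% (N=108).

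Arm size alone is therefore negligible.

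**Site share.** With q the share of one site, the SD of the between-arm difference is about √(4q(1−q)/N). At N=90 this is √(4 × 0.433 × 0.567 / 90) ≈ 0.104, and the mean absolute difference is about 0.104 × √(2/π) ≈ 0.083. Calculated without the approximation:

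| | N=90 | N=108 |
|---|---|---|
| Mean absolute difference | 8.4 points | 7.7 points |
| P(10 points or more) | 35% | 29% |
| P(20 points or more) | 6.1% | 3.6% |
| 95th percentile | 21 points | 19 points |

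**Effect on the PDC difference.** Shift = difference in site share × site gap. With a 0.10 gap at N=90:

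- typical: 0.084 × 0.10 ≈ 0.008, or 0.8 points;
- 95th percentile: 0.206 × 0.10 ≈ 0.021, or about 2 of the 15 margin points.

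The standard error of the arm difference is 0.286 × √(2/45) ≈ 0.060, so even the tail case is about a third of one standard error.

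**Power.** Simulated at N=90 with SD 0.286, no true arm difference and one-sided 0.05 (40,000 trials per cell, Monte Carlo standard error about 0.2 points):

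| Site gap in PDC | Current plan | Simple allocation, site-adjusted | Site-stratified and site-adjusted |
|---|---|---|---|
| 0 | 78.9% | 78.7% | 79.3% |
| 0.10 | 78.2% | 78.9% | 79.8% |
| 0.20 | 75.0% | 78.7% | 79.5% |

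The gain from the full change is about 0.5, 1.5 and 5 points after rounding. Simulated type I error under the current plan is 5.0–5.1% at every gap. Stratifying without adjusting makes the test conservative when the sites differ (4.1% at a 0.20 gap), which is why the analysis should match the randomisation.

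**The case against.** The strongest reply is that simple randomisation is a legitimate choice. Chance imbalance is random, the confidence interval already allows for it, and the type I error is preserved. It is also the least predictable scheme, which counts for something in an open-label trial where allocation happens at discharge. The demonstrated gain is small unless the sites differ a lot, and no document says that they do. All of this stands, and it limits the point to a cheap improvement.

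Several stronger readings are tempting, and the documents do not support them:

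- **That the result would be biased or confounded by site.** Allocation does not depend on site, so the imbalance is random and adds variance only.
- **That the sites use different pharmacies.** Two hospitals in different cities make this plausible, but the synopsis and Section 7.2 each refer to a single pharmacy source, and under Section 6 participants fill their own prescriptions.
- **That only one site pays participants.** Section 10.7 describes the card for one site and says nothing about the other. The card depends on completing visits, not on adherence, and is not tied to arm.
- **That the protocol expects adherence or cost to differ by site.** Section 4.1 speaks only of a more varied population and wider applicability.
- **That a shift of 2 margin points is to be expected.** It is a 95th-percentile imbalance multiplied by an assumed gap.

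It is also fair to say that the remedy is more than one added term: the tests named in Sections 9.3 and 9.4 take no covariate and would have to be replaced.

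**Conclusion.** The point holds as a low-severity improvement. The plan uses simple allocation at two sites and ignores site throughout the analysis, which leaves avoidable variance but no bias and no inflation of type I error. Under the assumed 70:90 enrolment split, a site-share difference of 10 points or more arises in roughly three allocations in ten. Its typical effect on the PDC difference is under 1 point for an assumed 10-point site gap. The loss of power at N=90 ranges from about 0.5 points (no gap) to about 5 points (a 0.20 gap), given an assumed SD of 0.286. The effect on the cost comparison could be larger or smaller, because the documents hold no site-level cost figures.

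**What to change.** **Randomisation.** Stratify by site, using permuted blocks of randomly varying size with the list concealed from recruiting staff. REDCap, already in use under Section 10.3.1, is a natural place for it. As an illustration, blocks of 4 hold the arm difference to at most 2 per site and 4 overall, and the difference in site share to about 4 points.

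**Analysis.** Use comparisons that match:

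- PDC: a linear model for mean PDC with arm and site, with the adjusted difference and its confidence interval set against the margin.
- Cost: a site-stratified (van Elteren) rank-sum test.
- Questionnaire scores: a linear model with arm and site.

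If enrolment has started, leave the randomisation alone and make only the analysis change, before any outcome is compared by arm.

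**Cost.** A new allocation list, and replacement text for the unadjusted tests in Sections 9.3 and 9.4. Allocation becomes slightly more predictable in an open-label trial, which varying block sizes and concealment limit. Adjustment without stratification gains nothing if the sites do not differ (78.7% against 78.9% power), 0.7 points at a 0.10 gap and 3.7 points at a 0.20 gap.

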1.1 Synopsis

Title: Comparison of Apixaban versus Enoxaparin for VTE Prevention after

Radical Cystectomy (the CARE trial)

Short Title: Comparison of Apixaban versus Enoxaparin (CARE)

Study Description:

Patients who have undergone radical cystectomy for bladder cancer will be randomized to receive a prescription for either enoxaparin or apixaban to self-administer at home until post operative day 30. Their adherence to the assigned medication will be the primary outcome. Comparisons of patient satisfaction, barriers to adherence, and cost will also be collected. The hypothesis is that adherence, satisfaction, and cost will be greater in the apixaban arm.

Objectives:

1. To compare rates of adherence to discharge on enoxaparin vs apixaban

a. Hypothesis: The apixaban group will exhibit non-inferior adherence, as measured by the proportion of prescribed medication accurately administered.

2. To compare costs of discharge on enoxaparin vs apixaban

a. Hypothesis: The median patient out-of-pocket cost, obtained from the institution's outpatient pharmacy data, is expected to be higher in the apixaban group compared to enoxaparin group.

3. To explore factors contributing to EP adherence

a. Hypothesis: it is anticipated that barriers to adherence to enoxaparin will primarily manifest as operational challenges and patient dissatisfaction, while for apixaban, they will predominantly arise from lack of insurance coverage and cost considerations. To evaluate these barriers, a combination of validated questionnaires and novel measures will be employed.

4. To collect safety and efficacy data on enoxaparin and apixaban

a. Considering that our study size will limit statistical power to detect risk reduction in venous thromboembolism (VTE) and/or bleeding events in either enoxaparin or apixaban, we will instead closely monitor and assess VTE and bleeding events in both treatment arms to contribute to existing studies for possible meta-analysis. This will be achieved

through the implementation of screening questions at each visit.

Primary Endpoint:

To address our primary objective, adherence, the primary endpoint will be measured as the proportion of days covered (PDC), ie the proportion of days between discharge and post operative day 30 during which the participant took their anticoagulant as prescribed.

Secondary Endpoints:

To address our secondary objective of comparing risk factors for adherence/non-adherence, secondary endpoints include:

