7.4 Drug Efficacy & Safety Assessments

In order to achieve the tertiary objective of collecting data regarding the efficacy and safety of both enoxaparin and apixaban when used as EP in the setting of radical cystectomy, we will directly enquire about instances of VTE and instances of bleeding. Screening questions for VTE and bleeding will be performed by study personnel and any positive screen will trigger review by one of the investigators, including review of the participant's medical record for results of imaging, labwork, notes from ED visits or inpatient admissions, or any other information deemed necessary by the investigator to confirm presence of VTE or bleeding and describe the outcome. This review will be conducted in accordance with HIPPA regulation. Review of the VTE or bleeding event will be performed for study documentation purposes; participants will be referred to their treating clinician for management of the VTE or bleeding, or if deemed necessary by the PI, to the emergency department for expedited care and their treating clinician notified of this for continued management.

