7.4.2 Assessing Bleeding

Bleeding events will be categorized as Major, Clinically-Relevant Non-Major (CRNM), and Minor. Major events and CRNM are defined according to the International Society on Thrombosis and Haemostasis (ISTH) Subcommittee of Scientific and Standardization Committee.^{32,33} Minor bleeding is defined as clinically overt bleeding that does not meet criteria for Major or CRNM bleeding.

To assess for Major and CRNM bleeding, participants will be directly asked if they have had bleeding that resulted in presentation to ED, inpatient admission, transfusion, or procedural intervention. To assess for Minor bleeding (or bleeding that is Major/CRNM but not yet diagnosed) participants will be asked about bruising or any other bothersome bleeding. All positive screens for bleeding events will be reviewed by a trial investigator to ensure appropriate clinical classification as Major, CRNM, or Minor. A positive screen will be reported to the investigators who will review the event as described above

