9.6 Analysis of Safety Endpoints

Given the well-established safety profile of both drugs and their use as SOC after cystectomy there is no formal safety endpoint for this study. However, both bleeding and VTE events will be solicited and tracked (see section 7) for safety analysis. DVT, PE, and a composite

outcome of the two will be compared between the two study arms using a test of proportions. For bleeding events, medical review of the chart by an investigator will determine if the event is Major, Clinically Relevant Non-Major (CRNM), or Minor (see section 7) and these three outcomes will be compared between the two groups as well as a composite outcome of Non-Minor Bleeding (Major and CRNM) using test of proportions.

These as well as any other adverse events will be graded (see section 7) and presented in a descriptive way with any further detail deemed clinically relevant by the PI (including but not limited to the treatment and outcome of the AE) included.

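### Section 4.1's reason for not blinding investigators does not cover the VTE and bleeding outcomes, which unmasked investigators confirm and grade before the arms are compared

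*Combined protocol and SAP*

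**What the plan says.** Section 4.1 states that "The randomization will be non-blinded" and gives one reason why this needs no remedy on the investigators' side: "Blinding of the investigators is not necessary given the outcomes are patient reported surveys and pill/vial counts". It adds that randomization deals adequately with bias.

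Section 3 lists two further endpoints as tertiary: "Rate of VTE, either PE or DVT" and "Rate of bleeding events, classified as major, clinically relevant nonmajor, or nonmajor". Under section 7.4, "any positive screen will trigger review by one of the investigators", who uses the medical record to confirm the event. Section 7.4.2 says that "All positive screens for bleeding events will be reviewed by a trial investigator to ensure appropriate clinical classification", and section 9.6 repeats that "medical review of the chart by an investigator will determine if the event is Major, Clinically Relevant Non-Major (CRNM), or Minor". Section 9.6 then compares the arms on DVT, PE, their composite, each of the three bleeding categories, and Major and CRNM bleeding combined. Section 9.1 makes all tests two-sided at 0.05.

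The synopsis (Objective 4) says that the study is too small to detect differences in these outcomes, and that the aim is to "assess VTE and bleeding events in both treatment arms to contribute to existing studies for possible meta-analysis".

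**The concern.** The reason in 4.1 describes only some of the trial's outcomes. For VTE and bleeding, the participant's report opens the file, and an investigator then decides what is counted and in which category. Randomization makes the arms comparable at allocation. It does nothing for a classification made weeks later by someone who can see which drug was prescribed.

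If bleeds were graded even slightly differently by arm, the CRNM, Minor and Major+CRNM comparisons would carry that difference. Low power in this trial is no protection, because the data are offered for pooling, and a pooled analysis takes in the estimate together with any bias in it.

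**Working it through.** The plan gives no figure on this point to reproduce. The check is a comparison of sections, followed by short arithmetic on how much one grading decision weighs.

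**1. Which outcomes does the reason in 4.1 cover?**

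| Outcome | Sections | How it is obtained | Investigator judgement |
|---|---|---|---|
| PDC | 3, 7.1, 9.3 | Participant's count of remaining doses, dates, prescription size | None |
| Medication adherence scale, satisfaction, COST | 7.1, 7.2 | Participant's answers | None |
| Medication cost | 7.2, 9.4 | Pharmacy records | None |
| DVT, PE, composite | 7.4, 7.4.1, 9.6 | Report of a diagnosed clot, then chart review | Confirmation, largely from imaging and notes |
| Major, CRNM, Minor, Major+CRNM | 7.4.2, 9.6 | Report of bleeding, then chart review | Assignment of category |

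The reason fits the first two rows. Cost falls outside its wording but needs no judgement. The last two rows give 3 + 4 = 7 between-arm comparisons, none of which is simply a survey score or a dose count.

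**2. Does the reviewing investigator know the arm?** The document does not say so outright. It follows from three things: the design is open-label, 4.1 decides against blinding investigators, and the review draws on a medical record that would show the prescribed drug. No section provides a masked reviewer, a redacted packet or an adjudication committee.

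**3. Where does the judgement matter most?** Section 7.4.2 defines Minor bleeding as whatever is overt but meets neither the Major nor the CRNM criteria. Moving one bleed across the CRNM/Minor line therefore changes three of the four bleeding comparisons (CRNM, Minor, Major+CRNM). Moving one across the Major/CRNM line changes two (Major, CRNM) and leaves the composite alone.

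**4. Weight of one decision.** Inputs: 108 enrolled (synopsis, 5.3) and 90 analysed, 45 per arm (5.3, 9.3.1). An even split of 108 gives 108/2 = 54 per arm; simple randomization makes this nominal.

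- Change in an arm's rate per regraded bleed = 1/n.
- n = 54: 1/54 = 1.85 percentage points.
- n = 45: 1/45 = 2.22 percentage points.

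The document gives no expected rate of non-minor bleeding, so a range is assumed. At 2%, 5% and 10% of 54 the expected counts are 1.08, 2.7 and 5.4, or about 1, 3 and 5 whole events. One regraded event changes those whole counts by 1/1 = 100%, 1/3 = 33% and 1/5 = 20%.

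**5. Could regrading alone produce a significant test?** This uses the pooled two-proportion z test, z = (b − a)/n ÷ √[p(1 − p)·2/n] with p = (a + b)/(2n), starting from equal assumed counts in the two arms.

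| Per arm | Events | Two-sided p |
|---|---|---|
| 54 | 3 v 9 | 0.066 |
| 54 | 3 v 10 | 0.038 |
| 45 | 3 v 9 | 0.063 |
| 45 | 3 v 10 | 0.036 |
| 54 | 5 v 13 | 0.039 |
| 45 | 5 v 13 | 0.035 |

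Starting from 3 v 3, seven bleeds in one arm would have to be upgraded to cross 0.05; from 5 v 5, eight. One or two regradings would not do it. What they would move is the estimated rate, which is what a meta-analysis uses.

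**The case against.** The case for leaving the plan alone is reasonable. Section 4 names adherence, satisfaction and cost as the objectives, and 4.1 follows directly, so its sentence was probably written with those in mind. Section 9.6 disclaims any formal safety endpoint. Major and CRNM bleeding follow published ISTH definitions, and the screening questions for them concern largely factual events such as emergency attendance, admission, transfusion or a procedure. Assessments are made by staff other than the treating physician (section 7), and a Medical Monitor who does not collaborate with the PI reviews adverse events (10.5). Masked grading would also leave participants' own reporting of bruising and bleeding open-label, and an injection-site bleed would reveal the arm.

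Much of this stands, and it limits the point to a minor one. It does not remove it. Section 3 lists these outcomes as endpoints and 9.6 tests them. Definitions narrow discretion without hiding the arm, and neither separation from the treating physician nor the Medical Monitor is masking.

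A reader might infer four stronger things that the document does not support:

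- **That the reviewers favour one drug.** Section 4.2 says that routine drug choice follows the prescriber's preference. It says nothing about the investigators who will review events.
- **That VTE is equally exposed.** The screen asks about a diagnosed clot, and confirmation draws on imaging and records, so there is less to judge.
- **That biased grading could never be put right.** Events rest on medical records and study data are kept (10.3.3), so a masked re-read before any pooling would be possible. Planning it now is simpler.
- **That 1.9 points measures the bias.** The same arithmetic holds under perfectly masked review.

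**Conclusion.** The point holds as a minor one. The reason given in 4.1 is incorrect for the tertiary VTE and bleeding outcomes, and seven planned comparisons depend on confirmation or grading by investigators who are not masked. The practical exposure lies mainly at the CRNM/Minor boundary and in the Major+CRNM composite. The PDC and questionnaire results are unaffected.

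The size of any bias cannot be estimated, because the document gives neither a bleeding rate nor a misclassification rate. What can be said is that each grading decision is worth about 1.9 to 2.2 percentage points in an arm. The conclusion rests on one inference, that the reviewer can see the assigned drug, and on a nominal 54 or 45 participants per arm.

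**What to change.** 1. **Section 4.1.** Limit the sentence on investigator blinding to PDC and the questionnaires, and say that VTE and bleeding are handled separately. Do not rely on randomization as the safeguard for these.
2. **Sections 7.4.2 and 9.6.** For each positive bleeding screen, the coordinator completes a fixed REDCap event form built on the ISTH criteria that 7.4.2 already cites: date, imaging result, haemoglobin, transfusion, intervention and care setting, with no drug name or route. An existing investigator at the other site assigns Major, CRNM or Minor from the form, and that category is the one analysed. Confirming VTE in the same way is optional.
3. **Unchanged.** Local clinical review and referral (7.4) and relatedness assessment against the drug label (10.4) stay unmasked.
4. **Limitation to state.** Participants' reporting of events remains open-label, and the coordinator who fills in the form is not masked.

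The cost is protocol wording, a short form, a little coordinator time per event, and a REDCap permission for cross-site reading, since 10.3.1 sets up site-specific access groups. No new staff are needed. Masking will sometimes fail, for example with injection-site bruising. If masked grading is declined, the correction to 4.1 and a stated limitation are the minimum.
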